6.6. Continued Access to Study Intervention after the End of the Study

Study completion will occur after all participants complete the follow up visit. Investigators will continue to follow SoA (Section [1.3](#)) for all participants until notified by Lilly that study completion has occurred.

Tirzepatide will not be made available after conclusion of the study to participants.

6.7. Treatment of Overdose

Study drug overdose (more than the specified number of injections) will be reported as an AE.

In the event of an overdose, the investigator should:

- Contact the medical monitor immediately.
- Evaluate the participant to determine, in consultation with the medical monitor, whether study drug should be interrupted or whether the dose should be reduced.
- Closely monitor the participant for any AE/SAE and laboratory abnormalities until study drug no longer has a clinical effect or can no longer be detected systemically (at least 30 days).

6.8. Concomitant Therapy

Participants will be permitted to use concomitant medications that they require during the study, except certain medications that may interfere with the assessment of efficacy and safety characteristics of the study treatments ([Table GPIM.2](#)).

Antihyperglycemic medications other than study drugs are ONLY allowed during these circumstances:

- for participants who require permanent discontinuation of tirzepatide but remain in the study.
- for rescue therapy after randomization due to severe, persistent hyperglycemia
- during the safety follow-up period.

GLP-1 RAs, DPP 4 inhibitors, pramlintide, and other basal insulins are prohibited medications and are not allowed during the study. Short-term treatment with a nonstudy insulin for up to 14 days is allowed for certain clinical situations, for example, elective surgery, during hospitalization, or hyperosmolar states (this will not be considered as rescue therapy).

Investigative site personnel will inform participants that they must consult with the investigator or a designated site personnel member upon being prescribed any new medications during the study. This may not be possible when initiated for treatment of medical emergencies, in which case, the participant will inform the investigator or a designated site personnel member as soon as possible. Any additional medication initiated during the course of the study (including over the counter [OTC] drugs, such as paracetamol or aspirin) must be documented, and the name of the drug and the date(s) of administration must be recorded on the “Concomitant Medications” section of the eCRF.

All nonstudy medications will be recorded on source documents at all visits.

Nonstudy medications taken by participants who are screened, but not randomized will not be reported to Lilly unless an SAE or AE occurs that the investigator believes may have been caused by a study procedure.

Table GPIM.2. Use of Concomitant Medications that May Interfere with Efficacy and Safety Assessments

Drug Class	Use During Screening/Lead-In	Conditions for Use after Randomization		
		Acute therapy ^a	Rescue therapy	During Safety Follow-Up Period
Drugs with approved weight loss indication ^b	Excluded	N	N/A	N
Systemic glucocorticoid therapy ^c	Excluded except for acute therapy ^a	Y	N/A	N (except for acute therapy ^a)
Antihyperglycemia medications				
GLP-1 RAs and related fixed-dose combination	Excluded	N	N	N
DPP-4 inhibitors and related fixed-dose combination	Excluded	N	N	N
Pramlintide	Excluded	N	N	N
Metformin ^d	Allowed	N/A	Y ^f	Y
SGLT-2i ^e	Allowed	N/A	Y ^f	Y
Insulins ^g	Excluded	Y	Y	Y
Meglitinides	Excluded	N	Y	Y
Alpha-glucosidase inhibitors	Excluded	N	Y	Y
Sulphonylureas	Excluded	N	Y	Y
Thiazolidinediones	Excluded	N	Y	Y

Abbreviations: DPP-4 = dipeptidyl peptidase-4; GLP-1 RA = glucagon-like peptide-1 receptor agonist; N = no; N/A = not applicable; SGLT-2i = sodium-glucose transporter 2 inhibitor; Y = yes.

^a Acute therapy = treatment for up to 14 days.

^b Wegovy[®] [semaglutide 2.4 mg], Saxenda [liraglutide 3.0 mg], Xenical[®] [orlistat], Meridia[®] [sibutramine], Acutrim[®] [phenylpropanolamine], Sanorex[®] [mazindol], Apidex[®] [phentermine], BELVIQ[®] [lorcaserin], Qsymia[™] [phentermine/topiramate combination], Contrave[®] [naltrexone/bupropion], or similar other body weight loss medications including over the counter (OTC) medications [for example, alli[®]]) within 3 months prior to Visit 1 or any time during the trial.

^c Chronic systemic glucocorticoid therapy (>14 days) should be excluded within 1 months prior to Visit 1, between Visits 1 and 3, and is not allowed during treatment period or safety follow-up period; does not apply to topical, intraocular, intranasal, intra-articular, or inhaled preparations.

^d Switching metformin manufacturers is allowed as long as the dose is the same, but changing to a metformin formulation with a different action profile (for example, from short-acting to long-acting metformin) is not permitted.

^e Switching SGLT-2i manufacturers is allowed as long as the dose is the same.

^f For rescue therapy, metformin and/or SGLT-2i dose can be increased if the dose is below maximum approved dose per country-specific label and is well tolerated.

^g Use of insulin glargine U100 is allowed during screening/lead-in period. For rescue therapy and therapy during safety follow-up period, use of other basal insulin except for insulin glargine U100 will not be allowed. Short-term treatment with a nonstudy insulin for up to 14 days is allowed for certain clinical situations, for example, elective surgery, during hospitalization, or hyperosmolar states (this will not be considered as rescue therapy).

7. Discontinuation of Study Intervention and Participant Discontinuation/Withdrawal

7.1. Discontinuation of Study Intervention

When necessary, a participant may be permanently discontinued from study drug. If so, the participant will remain in the study and complete all visits and procedures as shown in the SoA (Section 1.3). If the participant discontinues from study, the participant should complete an early discontinuation visit and post-treatment follow-up, if applicable, as shown in the SoA (Section 1.3).

7.1.1. Permanent Discontinuation from Study Intervention

Possible reasons leading to permanent discontinuation of investigational product:

- **Participant Decision**
 - the participant requests to discontinue investigational product.
- **Discontinuation due to a hepatic event or liver test abnormality.**
 - The study drug should be **interrupted** and close hepatic monitoring initiated (see Section 10.5.1) if one or more of these conditions occur:

Elevation	Exception
ALT or AST $>8\times$ ULN	
ALT or AST $>5\times$ ULN for more than 2 weeks	
ALT or AST $>3\times$ ULN and either TBL $>2\times$ ULN or INR >1.5	For participants with Gilbert's syndrome: If baseline direct bilirubin is >0.5 mg/dL, then doubling of direct bilirubin should be used for drug interruption decisions rather than TBL $>2\times$ ULN.
ALT or AST $>3\times$ ULN with the appearance of fatigue, nausea, vomiting, right upper quadrant pain or tenderness, fever, rash, and/or eosinophilia ($>5\%$)	
ALP $>3\times$ ULN, when the source of increased ALP is the liver	
ALP $>2.5\times$ ULN and TBL $>2\times$ ULN	For participants with Gilbert's syndrome: If baseline direct bilirubin is >0.5 mg/dL then doubling of direct bilirubin should be used for drug interruption decisions rather than TBL $>2\times$ ULN.
ALP $>2.5\times$ ULN with the appearance of fatigue, nausea, vomiting, right upper quadrant pain or tenderness, fever, rash, and/or eosinophilia ($>5\%$)	

Abbreviations: ALT = alanine aminotransferase; AST = aspartate aminotransferase; ALP = alkaline phosphatase;

INR = international normalized ratio; TBL = total bilirubin level; ULN = upper limit of normal.

Source: FDA Guidance for Industry: Drug-Induced Liver Injury: Premarketing Clinical Evaluation, July 2009 and other consensus guidelines, with minor modifications

- Resumption of the study drug can be considered only in consultation with the Lilly designated medical monitor and only if the liver test results return to baseline and if a self-limited nondrug etiology is identified.

- Otherwise, the study drug should be discontinued if a self-limited nondrug etiology cannot be identified.

In addition, participants will be discontinued from the investigational product in the following circumstances:

- If a participant is inadvertently enrolled and it is determined that continued treatment with study drug would not be medically appropriate
- Acute or chronic pancreatitis
- If a participant is diagnosed with MTC after randomization, or has post randomization calcitonin value ≥ 35 ng/L that has increased at least 50% over baseline
- If a participant is diagnosed with an active or untreated malignancy (other than basal or squamous cell skin cancer, in situ carcinomas of the cervix, or in situ prostate cancer) after randomization
- Any significant study drug -related hypersensitivity reaction
- Any other Treatment emergent adverse event (TEAE), SAE, or clinically significant laboratory value for which the investigator believes that permanent study drug discontinuation is the appropriate measure to be taken
- If female participant becomes pregnant
- If a participant is diagnosed with T1DM

Participants who stop the study drug permanently will receive another glucose-lowering intervention (Section 6.8) and will continue participating in the trial according to the protocol to collect all planned efficacy and safety measurements.

Participants discontinuing from the investigational product prematurely for any reason should complete adverse event and other follow-up procedures per Section 1.3 (SoA), Section 8.3 (Adverse Events), and Section 8.2 (Safety) of this protocol.

7.1.2. Temporary Interruption of Study Intervention

In certain situations after randomization, the investigator may need to temporarily interrupt study drug. Every effort should be made by the investigator to maintain participants on study drug and to restart study drug after any temporary interruption, as soon as it is safe to do so.

If study drug interruption is...	then...
≤ 2 consecutive doses	the treatment can be restarted at the same dose if the drug was well tolerated prior to discontinuation.
≥ 3 consecutive doses	the IWRS will dispense 5 mg/matched placebo and escalated as required by protocol.
due to AE	the event is to be documented and followed according to the procedures in Section 8.3 of this protocol.

due to intolerable persistent GI AE (eg: nausea, vomiting, or diarrhea)	the participants should be treated as suggested in Section 6.5.1.1 .
---	--

Abbreviations: AE = adverse event; GI = gastrointestinal; IWRS = interactive web response service.

Investigators should inform Lilly that study drug has been temporarily interrupted.

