6.1.1. Tirzepatide Dosing

The starting dose of tirzepatide will be 2.5 mg QW for 4 weeks, followed by an increase to 5 mg QW, for the duration of the study in the 5-mg group.

For the 10-mg group, the starting dose of tirzepatide will be 2.5 mg QW for 4 weeks, then the dose will be increased by 2.5 mg every 4 weeks (2.5 to 5 to 7.5 to 10 mg) until the 10-mg dose is reached and maintained for the duration of the study.

For the 15-mg group, the starting dose of tirzepatide will be 2.5 mg QW for 4 weeks, then the dose will be increased by 2.5 mg every 4 weeks (2.5 to 5 to 7.5 to 10 to 12.5 to 15 mg) until the 15-mg dose is reached and maintained for the duration of the study.

Figure GPIM.1 illustrates the tirzepatide dose escalation regimen.

Abbreviations: Met = metformin; QW = once weekly; SGLT-2i = sodium-glucose transport protein 2 inhibitor.

Figure GPIM.1. Tirzepatide Dose Escalation

There are no restrictions on the time of day each weekly dose of study drug is given, but it is advisable to administer the subcutaneous (SC) injections on the same day and same time each week. The actual date and time of all dose administrations will be recorded by the participant. If a dose of study drug is missed, the participant should take it as soon as possible unless it is within 72 hours of the next scheduled dose, in which case, that dose should be skipped and the next dose should be taken at the appropriate time. The day of weekly administration can be changed if necessary, as long as the last dose was administered 72 or more hours before.

All participants will inject study drug subcutaneously in the abdomen or thigh using the SDP; a caregiver may administer the injection in the participant's upper arm. A new SDP will be used for each injection. If study drug is to always be injected in the same body region, participants should be advised to use a different injection site each week.

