6.5. Dose Modification

6.5.1. Tirzepatide

Please refer to Section 6.1.1 for tirzepatide administration. Study drug dose modification is not permitted except for management of intolerable GI symptoms (see Section 6.5.1.1).

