6.5.1.1. Management of Participants with Gastrointestinal Symptoms

In participants who experience intolerable Gastrointestinal symptoms (for example, nausea, vomiting, or diarrhea) at any time during the study, the following measures are recommended:

1. counseling on dietary behaviors that may help mitigate nausea and vomiting, (for example, eating smaller meals, splitting 3 daily meals into 4 or more smaller ones, and stopping eating when they feel full).
2. if symptoms persist despite #1, prescribing symptomatic medication (for example, antiemetic or antidiarrheal medication), at the investigator's discretion
3. if symptoms persist despite #1 and #2, interrupting study drug for 1 dose, provided the participant has taken the last 3 weekly doses. Study treatment should be resumed at the assigned dose immediately, either alone or in combination with symptomatic medication, which can also be utilized to manage symptoms (Section 6.8). Management of study drug after interruptions >1 dose is discussed in Section 7.1.2.

If intolerable GI symptoms (for example, nausea, vomiting, or diarrhea) persist despite the above measures after Visit 11 (after the scheduled visit in Week 8) the investigator should contact Lilly to consider continuing treatment at a lower maintenance dose of study drug in a blinded fashion, for example:

- Participants at 5 mg will decrease the dose to placebo.
- Participants at 7.5 mg or 10 mg will decrease the dose to 5 mg.
- Participants at 12.5 mg or 15 mg will decrease the dose to 10mg.

If de-escalation of the tirzepatide dose is necessary, the investigator will use the interactive web-response system (IWRS) to receive the appropriate tirzepatide dispensing information. If de-escalation is needed between scheduled visits, the IWRS will have unscheduled visits (for example, Visit 13a) dedicated to provide dispensing information for participants whose dose has been de-escalated. Those participants who have their dose de-escalated, will not be escalated again. The dose can be de-escalated only once. After that, the participants will have to discontinue study drug if intolerable GI AE persists and stay in the study.

If intolerable persistent GI symptoms occur, the investigator should take the above measures to keep the participant on study treatment. However, after the escalation period (Week 24), dose decreases will not be allowed.

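### The restart rule after three or more missed doses is not reconciled with the dose-modification and de-escalation rules

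*Protocol*

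**What the plan says.** Protocol 7.1.2 sets the restart by the length of the gap. After one or two missed doses, "the treatment can be restarted at the same dose if the drug was well tolerated prior to discontinuation". After three or more, "the IWRS will dispense 5 mg/matched placebo and escalated as required by protocol". That second row carries no condition on the reason for the gap, the study week, the randomized dose or any earlier reduction. A further row covers persistent GI intolerance: "the participants should be treated as suggested in Section" 6.5.1.1.

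Three other sections govern the same dose:

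- **Protocol 6.5.1:** "Study drug dose modification is not permitted except for management of intolerable GI symptoms".
- **Protocol 6.5.1.1:** after the Week 8 visit, a participant with persistent intolerance may be reduced once, from 12.5 or 15 mg to 10 mg, or from 7.5 or 10 mg to 5 mg. At the lowest level, "Participants at 5 mg will decrease the dose to placebo". Then, "Those participants who have their dose de-escalated, will not be escalated again". No decrease is allowed after Week 24. For gaps of more than one dose the section refers the reader to 7.1.2.
- **Protocol 6.1.1:** for the 5 mg group, "The starting dose of tirzepatide will be 2.5 mg QW for 4 weeks, followed by an increase to 5 mg QW". The 10 mg and 15 mg groups start the same way and rise by 2.5 mg every 4 weeks.

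On the analysis side, SAP 4.1 assigns participants to their randomized maintenance dose whatever they received. SAP 4.6.1 makes the listing of participants who re-initiate after three or more missed doses optional and does not ask for the restart dose.

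**The concern.** Dispensing is blinded and runs through the interactive web-response system (IWRS), so the dose a restarting participant receives depends on which section was programmed. A site cannot readily see a discrepancy.

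The protocol itself foresees interruptions unrelated to GI symptoms: liver test abnormalities (7.1.1), a calcitonin recheck after washout of another drug (8.3.4.4) and suspected severe allergic reactions (8.3.4.7). Any of these could outlast three weekly doses. It also creates a group of already-reduced participants for whom the restart rule has no stated exception.

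Two things are at stake: the safety of people restarting treatment, some of whom have already shown intolerance, and knowledge of what dose the 10 mg and 15 mg groups received. Those two groups carry the primary comparison.

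**Working it through.** The plan gives no figure on this point to reproduce. The check compares the sections and lays the 6.1.1 schedule against a 5 mg restart.

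**Inputs.** First dose at Visit 3, Week 0 (Protocol 4.1.1); 4-week steps of 2.5 mg (6.1.1); restart at 5 mg after at least three missed doses (7.1.2). Assumption: weekly doses run from Week 0 to Week 39.

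**Step 1. Scheduled dose by week.** A group reaches its assigned dose at 4 × (number of steps): 4 × 1 = Week 4, 4 × 3 = Week 12 and 4 × 5 = Week 20.

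| Weeks | 5 mg group | 10 mg group | 15 mg group |
|---|---|---|---|
| 0–3 | 2.5 | 2.5 | 2.5 |
| 4–7 | 5 | 5 | 5 |
| 8–11 | 5 | 7.5 | 7.5 |
| 12–15 | 5 | 10 | 10 |
| 16–19 | 5 | 10 | 12.5 |
| 20–39 | 5 | 10 | 15 |

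**Step 2. Earliest restart.** With dose 1 taken at Week 0, the first possible run of three missed doses is Weeks 1, 2 and 3, so the earliest restart is Week 4. The schedule is then already 5 mg in every tirzepatide group.

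**Step 3. Non-GI interruptions.** In the 5 mg group the restart always equals the scheduled dose. In the 10 mg and 15 mg groups it equals the schedule through Week 7 and lies below it from Week 8. Against the last dose taken, rather than the schedule, the first cut comes at Week 12: 7.5 mg at Week 8, Weeks 9 to 11 missed, 5 mg at Week 12. Section 6.5.1 has one exception, GI intolerance, so it does not permit this change, while 7.1.2 orders it.

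**Step 4. Participants already reduced.**

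| Current dose | Literal effect of 7.1.2 | Conflict with 6.5.1.1 |
|---|---|---|
| 10 mg | Down to 5 mg, then up | Second reduction, then a barred escalation |
| 5 mg | 5 mg, then up | Barred escalation, unless the closing words of 7.1.2 import the bar |
| Placebo | 5 mg or matched placebo; text does not say which | Barred escalation if active drug is dispensed |

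**Step 5. GI interruptions after Week 24.** Two rows of the 7.1.2 table apply. One orders 5 mg, which is a decrease for anyone on 10 or 15 mg. The other leads to 6.5.1.1, which bars decreases by then. Section 6.5.1.1 in turn sends gaps of more than one dose back to 7.1.2. Neither section states precedence.

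**Step 6. Time back to the assigned dose.** From 5 mg, the 10 mg group needs two steps (2 × 4 = 8 weeks) and the 15 mg group four (4 × 4 = 16 weeks). To receive at least one assigned dose by Week 39, the latest restart is 39 − 8 = Week 31 for 10 mg and 39 − 16 = Week 23 for 15 mg. A 15 mg participant restarting at Week 24 would take 5 mg in Weeks 24–27, 7.5 mg in 28–31, 10 mg in 32–35 and 12.5 mg in 36–39.

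**Step 7. What the analysis records.** SAP 1.1 treats permanent discontinuation and rescue as intercurrent events, not temporary interruption. Restarted participants therefore stay in the efficacy analysis set under their randomized dose. SAP 6.2 counts injections toward compliance regardless of dose.

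**The case against.** The best defense is that 7.1.2 is a specific rule and 6.5.1 a general one, so the specific rule governs and only a cross-reference is missing. The sections are linked, since 6.5.1.1 points to 7.1.2. This is a reasonable reading, but 6.5.1 states its single exception in closed terms and nothing in the text gives 7.1.2 priority.

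For participants already reduced, the closing words of the restart rule may import the bar on escalation, and the mention of matched placebo may cover someone moved to placebo. Both readings are open. A reader might therefore go too far in inferring that a participant on placebo would certainly receive active 5 mg, or that no site could ever satisfy both rules; the documents support neither. The softer readings do not settle the participant reduced to 10 mg, whose 5 mg restart is a second decrease whether or not escalation follows. Section 6.5.1.1 also requires stopping study drug if intolerable GI events persist after one reduction, so this conflict is clearest when such a participant later misses doses for another reason.

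A reader might also infer a clash with the starting dose, since someone missing Weeks 1 to 3 goes from one 2.5 mg dose to 5 mg. Step 2 shows otherwise: 5 mg is by then the scheduled dose, and the rise is the ordinary first step. What remains is an ambiguity over whether the 4 weeks in 6.1.1 means calendar time or doses taken.

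Investigators are asked to inform the sponsor of interruptions and to contact it about reductions, which lowers the chance that a wrong dispense goes unnoticed. It does not settle the wording.

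**Conclusion.** The inconsistency stands in two situations: non-GI interruptions of three or more doses in the 10 mg and 15 mg groups from Week 8, and participants already reduced. A third gap is the unstated precedence for GI interruptions after Week 24.

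The measurable consequence is the 8 or 16 weeks needed to regain the assigned dose. Restarts from Week 32 (10 mg) or Week 24 (15 mg) yield no assigned dose by Week 39. Those delays follow from 7.1.2 alone and are not themselves evidence of contradiction; they show what depends on the rule chosen.

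The result rests on the literal wording, 4-week steps after restart, and weekly dosing through Week 39. The documents give neither the number of participants affected nor the IWRS specification. They therefore do not support an inference that the primary comparison is materially biased or that wrong doses were dispensed. This is a point of wording and dispensing logic that should be corrected because it bears on safety and is cheap to resolve.

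**What to change.** Reconcile Protocol 6.5.1, 6.5.1.1 and 7.1.2:

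- Make 6.5.1 and 7.1.2 agree on restarts after non-GI interruptions.
- State which rule governs a participant already reduced, separately for those on 10 mg, 5 mg and placebo.
- State which section prevails for GI interruptions after Week 24.

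Then check that the IWRS logic matches the reconciled text. Which dose or rule applies is for the sponsor's clinical team.

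In SAP 4.6.1, make the listing of re-initiations after three or more missed doses firm, and add restart week, restart dose and dose at Week 40. If dosing has already finished, which the documents do not say, record what the IWRS actually dispensed to these participants.

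The cost is a protocol clarification, an IWRS check and one SAP listing. Sample size and the primary model are unchanged.
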